6.3 Control Study Arm

Participants assigned to the control condition will be administered the baseline and 8-week follow-up surveys. After that, they will be invited to take part in the STEP-UP intervention but will not receive any additional incentive for participating in the intervention, and they will not have additional outcome data collected (meaning the participants will not complete any additional study surveys when participating in the STEP-UP program after their 8-week follow up survey). Process intervention data will be tracked for all control group members who opt to do STEP-UP, such as completion of CHW orientation and subsequent telephone sessions.

6.4 Measures to Minimize Bias: Randomization and Blinding

Participants will be randomized to intervention or control groups using a block randomization scheme with randomly selected block sizes. The study team member who randomizes participants will be blinded to participant responses on the baseline assessment and will only be informed if the assessments were completed. Participants will be informed by the study team of their study arm assignment and will be informed of next steps for their study arm.

6.5 Study Intervention Adherence

Attendance of community health worker sessions (or responding to phone calls/texts during weeks where there is no session) will be the main mechanism of tracking adherence. Community health workers will also log information from participant reports about working towards their goals during their calls. We will assess self-report of listening to podcast episodes (0 to 5).

6.6 Concomitant Treatment

This study will not restrict participation in other types of treatments. However, participants in the STEP-UP study will not be able to participate in our other ongoing R01 studies, Re-Engaging in Self-Care and Enjoying Today (RESET), and the original STEPS intervention trial. These two studies are recruiting from a similar population and have some overlapping intervention components. We will make this clear in the recruitment process.

6.7 Lifestyle Considerations

This study does not have any restrictions regarding lifestyle and/or diet.

6.8 Intervention Discontinuation

We will end a subject's participation upon their request. The research team may end a subject's participation from the study if they are too acutely ill to participate or have a change in disease severity in which the study team (in consultation with [name] of Weill Cornell Medicine) feels that they should not take part in the intervention. These instances will be recorded as adverse events, and all participants will be contacted to determine if they can complete outcome assessments if possible. We may also end a subject's participation if the research team deems that the participant is not a good fit for the program (e.g., belligerent with staff, too difficult to contact, or confused by study procedures).

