5.2 Exclusion Criteria

- Hospitalization in the last month
- Planned major surgery in the next three months that would interfere with program participation (e.g., knee or hip replacement)
- Current or previous participation in either the STEPS or RESET interventions
- Severe cognitive impairment or other severe physical or psychiatric disorder judged by the study team to pose a significant barrier to participation

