During the verbal consent process, the interviewer will read the informed consent document aloud, stopping to ask questions after each section. The verbal consent is documented in three ways. 1) With the participant's permission, we will audiorecord the verbal consent interaction (using UM Zoom or UM Zoom Phone) and securely store the audiofiles in access-restricted UM Dropbox folders. 2) We write their full name, the date, and the interviewer's initials to document that verbal consent was obtained in REDCap. 3) We will also indicate in REDCap that verbal consent was provided and document the date.

For participants who choose to have the consent document mailed to them first, research staff will call potential participants approximately one week after mailing the consent document to go through the verbal consent process over the phone and answer any questions. If the participant preferred an emailed copy of the consent document, research staff may call sooner based on the participants preferences.

Upon completing verbal consent, the participants will be enrolled in the study and will be scheduled for a baseline interview.

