5.5 Screen Failures

Individuals who sign the consent document and who subsequently are deemed ineligible or inappropriate for participation (e.g., unable to participate meaningfully in study activities, discovery that diagnoses are not consistent with study criteria, etc.) will *not be enrolled*, but instead classified as "screen failures."

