6.10 Withdrawal from the Study

If participants withdraw or decline to finish the intervention, every effort should be made to gather primary outcome data (pain interference) as well as a query about adverse events.

- The goal is to collect the information as close to the designated follow-up assessment as possible (8 weeks). Participants need to complete the assessment within one month of the follow-up date in order to be counted as non-missing.
- For intervention group participants wishing to discontinue participation in the intervention, the study team member will ask to call them during the scheduled follow-up window.
- Participants who state that they wish to withdraw completely from the study will not be contacted further.

The reason for participant discontinuation or withdrawal from the study will be recorded in REDCap. Participants who sign the informed consent form and are randomized to the intervention but do not begin it will not be replaced, due to the short overall study period. Participants who sign the informed consent form, and are randomized and receive the study intervention, and subsequently withdraw, or are discontinued from the study, will not be replaced.

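### Removal for poor fit, and withdrawal of non-starters, carry no stated 8-week follow-up and fall mainly on the intervention arm

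*Combined protocol and SAP*

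**What the plan says.** The last sentence of Section 6.8 allows the team to end a subject's participation "if the research team deems that the participant is not a good fit for the program". The criteria are three examples: "belligerent with staff, too difficult to contact, or confused by study procedures". The sentence has no time limit and names no arm.

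Earlier in the same section, for participants stopped because of acute illness or a change in disease severity, the plan says that "all participants will be contacted to determine if they can complete outcome assessments if possible". Section 6.10 adds: "If participants withdraw or decline to finish the intervention, every effort should be made to gather primary outcome data". It respects complete withdrawal and does not replace randomized participants who leave.

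A note under the schedule in Section 7.1 says that the team withdraws from the study anyone who has not started the intervention within one month of the baseline assessment. The same note invites people who drop out of the intervention to complete the surveys and labels this intent to treat.

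Section 11.2.3 says that everyone randomized to the intervention group will be included. The model in Section 11.2.2 takes the 8-week value as its dependent variable.

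On entry to the trial, Section 5.4 says: "Upon completing verbal consent, the participants will be enrolled in the study and will be scheduled for a baseline interview". Section 5.5 classes as screen failures, and as not enrolled, "Individuals who sign the consent document and who subsequently are deemed ineligible or inappropriate for participation".

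**The concern.** The test in 6.8 is fit for the program, and before the endpoint only one arm has a program. Difficulty of contact or confusion therefore has many more occasions to be noticed in the intervention arm. Section 6.4 describes no blinding of the people who make this judgement.

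If those removed are not surveyed at week 8, the intervention arm loses outcomes selectively. People who are hard to reach or confused may well be those least likely to improve. Losing them would then flatter STEP-UP on pain interference, both in the adjusted mean and in the share reaching the minimally important difference. Engagement and satisfaction are secondary endpoints of this pilot, so it also matters that such cases remain visible in the feasibility results.

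**Working it through.** **Step 1. Ways out of the trial after randomization, and whether an outcome attempt is stated.**

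| Route | Where | Outcome attempt stated? |
|---|---|---|
| Acute illness or change in severity | 6.8 | Yes |
| Participant withdraws or declines to finish | 6.10 | Yes, unless withdrawal is complete |
| Drops out of the intervention | 7.1 note | Yes, invited to the surveys |
| Team judges poor fit | 6.8, last sentence | No |
| Not started within one month of baseline | 7.1 note | No; withdrawn from the study |

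The two routes without an outcome attempt are the two that the team initiates for reasons other than illness.

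**Step 2. Exposure by arm before the endpoint.** The intervention arm has six weekly sessions (6.2) plus reminders, then the 8-week survey. Controls have the 8-week survey and are offered the program only afterwards (6.3). Leaving reminders out, that is 6 + 1 = 7 scheduled contacts against 1. Suppose each contact has the same chance p of triggering removal (an assumption). The chance of removal is then 1 − (1 − p)^7 against p:

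- p = 1%: 6.8% against 1%, ratio 6.8
- p = 2%: 13.2% against 2%, ratio 6.6
- p = 5%: 30.2% against 5%, ratio 6.0

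The one-month non-start rule needs no such assumption. Controls cannot start the program before their 8-week survey, so in the endpoint period the rule can operate only in the intervention arm.

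**Step 3. What the analysis does with these people.** The model in 11.2.2 needs the 8-week value, and no missing-data method is given. A removed participant without a survey contributes nothing to it, whatever 11.2.3 says about inclusion.

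**Step 4. Illustrative size.** The plan gives no expected removal rate and no power calculation, so there is no stated figure to reproduce. Inputs:

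- Arm size: 40 participants at 1:1, so 20 per arm; one removal is 1/20 = 5%.
- k: number removed from the intervention arm only (assumed).
- D: how many T-score points worse they would have scored than those kept (assumed, 5 to 10).

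Apparent benefit with no true effect = (k/20) × D:

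| k | D = 5 | D = 10 |
|---|---|---|
| 1 | 0.25 | 0.5 |
| 2 | 0.5 | 1.0 |
| 3 | 0.75 | 1.5 |
| 4 | 1.0 | 2.0 |

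The important difference is 2.5 points in the Section 2 table and 3 points in 11.2.2. Two to four removals therefore give between 0.5/3 = 17% and 2.0/2.5 = 80% of it. Equal removal in both arms with the same D would cancel.

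**Step 5. Cross-check.** Let fit correlate with outcome at ρ, and remove the least suitable fraction f. The shift is ρ × SD × φ(z_f)/(1 − f), where φ is the standard normal density and z_f its f-quantile. Take ρ from 0.3 to 0.5 (assumed) and SD from 7 (assumed) to 10 (the T-score reference in 11.2.2):

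- f = 5%: 0.23 to 0.54 points
- f = 10%: 0.41 to 0.97 points
- f = 20%: 0.73 to 1.75 points

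These ranges agree closely with one, two and four removals in Step 4.

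**The case against.** The strongest reply is that 6.8 is headed as intervention discontinuation and its test is fit for the program. The illness sentence speaks of leaving the study; the poor-fit sentence does not. It can be read as ending program contact only, with follow-up continuing. That reading is available and is close to the fix, but the text does not state it. It is not available for non-starters, whom 7.1 withdraws from the study outright.

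The plan also has protections: the intent-to-treat statement, no replacement, recorded reasons for leaving, and the survey invitation to people who drop out. These stand, but none names a participant removed by the team, and none supplies a missing 8-week value.

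Someone truly unreachable may have no survey under any rule. That also stands, so part of the loss cannot be put down to 6.8. Section 5.6 nevertheless sets a defined effort for the follow-up survey (five attempts, a letter, five more), and it should apply equally here.

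The trial is a pilot and is declared unpowered. This limits what can be claimed about significance. It does not make a biased effect estimate or responder comparison harmless.

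Three stronger readings are tempting but unsupported:

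- **Removal strikes one arm only.** Section 6.8 covers any subject, and its examples can appear in survey calls in either arm. The text supports unequal opportunity.
- **Randomized people can be relabelled screen failures.** Section 5.5 never mentions randomization, which follows the baseline survey (7.2), so its natural window is before the arm is known. What is missing is an explicit cut-off.
- **The poor-fit examples repeat the judgement in 5.2.** That exclusion, "judged by the study team to pose a significant barrier to participation", is confined to severe impairment or disorder. Belligerence and difficulty of contact are neither.

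**Conclusion.** The point holds as a gap in follow-up with unequal exposure by arm. Two team-initiated routes carry no stated outcome attempt. One falls mainly on the intervention arm, and the other can fall only there before week 8. The non-start rule also sits badly with the effort in 6.10 to collect outcomes and with the inclusion promise in 11.2.3; these passages must be reconciled.

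The sizes in the working depend on assumed numbers of removals, on removed people scoring worse, and on their 8-week values being missing. They show that a few cases could matter in arms of 20. They do not predict that this will happen.

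A reader might also infer that session completion would be reported only for those retained. Nothing in Section 2 or 11.2.2 restricts the denominator in that way; the plan simply does not say how these cases count. The conflict between 5.4 and 5.5 over when a person is enrolled is real but editorial.

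**What to change.** In 6.8 and in the 7.1 note, state that a poor-fit decision or a failure to start ends program contact only. State that the 8-week survey is still attempted under the 5.6 contact rules unless the participant withdraws completely. This leaves the team's discretion over program contact as it is.

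In 11.2.2, state that everyone randomized to the intervention stays in the engagement denominator, with these cases counted by the sessions they actually completed.

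As a clarification, state in 5.5 that screen-failure status ends at randomization, and reconcile 5.4 with 5.5 on the point of enrollment.

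The cost is a few sentences, a few extra survey calls and possibly lower reported engagement.

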6.9 Treatment Fidelity

6.9.1 Overall compliance

See **6.5 Study Intervention Adherence** above.

6.9.2 Community Health Worker Training and Tracking

The study CHW will complete the MiCHWA CHW Certification Training Program, a 126-hour course covering topics such as: communication skills and motivational interviewing, documentation and reporting, navigating community resources, and healthy lifestyles.

STEP-UP-specific training will take place over a series of initial training sessions (the equivalent of approximately 4 full days) with ongoing training/feedback by the PI or other members of the study team or research staff throughout the study period. Our CHW training approach has been refined over a series of studies, and emphasizes role play and practice sessions with feedback. We focus on older adults' needs, including multimorbidity and cognitive issues, as well as record-keeping, teaching goal-setting, managing common issues such as temporary increases in pain after activity, and knowing when to consult with a supervisor and the study team.

All intervention sessions with participants will be audio recorded, with participants' permission, and a checklist will be used to determine fidelity to the session protocol in the community health worker STEP-UP manual. We will test for CHW "drift" from the protocol by listening to all sessions for the first 3 participants, and a random 20% of recorded calls thereafter, and offer feedback and additional training as needed. Recording of session information in REDCap (e.g., information from phone sessions such as goals, also reminder calls/texts and whether response was received from participant) will also be audited, on the same schedule. The CHW will meet regularly (weekly or biweekly) with a research staff member for coaching and feedback. The duration of calls will also be recorded.

6.10 Withdrawal from the Study

If participants withdraw or decline to finish the intervention, every effort should be made to gather primary outcome data (pain interference) as well as a query about adverse events.

- The goal is to collect the information as close to the designated follow-up assessment as possible (8 weeks). Participants need to complete the assessment within one month of the follow-up date in order to be counted as non-missing.
- For intervention group participants wishing to discontinue participation in the intervention, the study team member will ask to call them during the scheduled follow-up window.
- Participants who state that they wish to withdraw completely from the study will not be contacted further.

The reason for participant discontinuation or withdrawal from the study will be recorded in REDCap. Participants who sign the informed consent form and are randomized to the intervention but do not begin it will not be replaced, due to the short overall study period. Participants who sign the informed consent form, and are randomized and receive the study intervention, and subsequently withdraw, or are discontinued from the study, will not be replaced.

6.11 Lost to Follow-up

A participant will be considered lost to follow-up per the protocol presented in 4.6.

7 STUDY PROCEDURES

7.1 Schedule of Activities

Activity	Weeks									
	Pre	0	1	2	3	4	5	6	7	8
Eligibility Screening	X									
Consent Process	X									
Randomization	X									
Demographics		X								
Chronic conditions and overall health		X								
Pain Interference (PROMIS-43 6-item scale)		X								X
PROMIS-29 +2 ^{14,15} (except Pain Interference subscale)		X								X
Pain Intensity (Numerical Rating Scale)		X								X
Pain Self-Efficacy Questionnaire		X								X
Pain Medication Use		X								X
Communication with Provider		X								X
Chronic Pain Acceptance		X								X
Physical Activity		X								X
Fear of Movement		X								X
Patient Activation Measure		X								X
Survey of Pain Attitudes (SOPA) - Control subscale		X								X
Pain Catastrophizing Scale		X								X
Life Control Scale		X								X
PROMIS Meaning and Purpose (4-item)		X								X
Global impression of change in pain, functioning, quality of life, and use of pain medication										X
STEP-UP Program Evaluation Questions (intervention group only; both close- and open-ended)										X

STEP-UP: CHW sessions (intervention group only)				X	X	X	X	X	X		
---	--	--	--	---	---	---	---	---	---	--	--

Notes:

*Shaded rows represent measures on the telephone data collection surveys (at baseline and/or 8 weeks).

**Primary and secondary outcomes are bolded.

***Allowable assessment windows: Participants need to complete the assessment within one month of the follow-up due date to be counted as non-missing.

****If participant does not start intervention within one month of baseline assessment, they will be withdrawn from the study by the study team. If a participant drops out of the intervention, they will be invited to complete the surveys if they want to (intent to treat) or they can withdraw from the study.

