7.2 Description of Activities

- *Telephone data collection surveys* – participants will complete the validated measures tested as outcomes or mediators listed above as well as other measures to help characterize health and functional status, quality of life, and satisfaction with the intervention, at baseline and/or 8 weeks from baseline. Participants will be sent response options for each of the survey scales prior to their scheduled telephone survey appointment so they can see the response options and follow along. If participants do not have the survey scales, they can either reschedule or continue with the survey if they prefer (staff will read responses for each question/item on the survey).
- *Randomization* – occurs after a participant completes their baseline telephone survey.
- *STEP-UP Program (Intervention)* – See Table in Section 6.2 for details of intervention activities and flow..

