11.2.2 Primary & Secondary Endpoints

We will calculate baseline descriptive statistics and compare groups using independent-sample t-tests for continuous variables and chi-squared tests for categorical variables. We will assess psychometrics of scales used (e.g., internal consistency reliability and concurrent validity). We will convert the PROMIS 6-item Pain Interference subscale score to T-scores (a standardized score with a mean of 50 and SD of 10) by summing the scales and using the conversion tables provided at HealthMeasures.net.

To assess the effect of being in the intervention group, we will use a univariate analysis of variance model for continuous primary and secondary outcomes. The dependent variable in each model will be the value of the outcome at 8-week follow-up; the independent factor will be treatment group (intervention vs. control), with the baseline value of the outcome as a covariate.

Effect size will be indicated by partial eta squared for the treatment group variable. In order to assess the potential clinical relevance of the intervention, we will use chi-squared tests to compare the percentage of participants in each treatment condition who achieved the Minimally Important Difference (MID) of ≥ 3 T-score points in PROMIS pain interference.

We will repeat this analysis with the secondary outcomes: Global Impression of Change in Pain and Functioning. Transformations for non-normality of outcomes will be performed as indicated.

We will also assess the moderating effect of selected variables such as sex, age, baseline pain intensity, and degree of program engagement. Moderation analyses will use standard approaches to evaluate interactions between these covariates and treatment group.

For patient engagement, the secondary outcome indicating feasibility that is composed of: 1) number of sessions completed out of 7; and 2) participant satisfaction on a 5-point Likert scale, we will calculate descriptive statistics. We will also explore differences by age group (under 65/65+) as well as gender. As an exploratory analysis, we will investigate whether satisfaction differs according to whether or not participants achieved the MID on the primary outcome of pain interference.

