11.2.3 Other Pre-specified Analyses

To explore potential mechanisms, we will examine the association between: 1) participation in the intervention and the hypothesized composite mediator, Perceived Control Over Pain, as well as each of the 4 component scales (Survey of Pain Attitudes Control subscale, Pain Catastrophizing Scale, Life Control scale, and PROMIS Meaning and Purpose); and 2) between mediators and outcomes. Positive correlations in both cases will provide evidence for a potential mediating effect.

Following intent-to-treat principles, we will include all participants randomized to the intervention group, with sensitivity analyses assessing whether different levels of participant engagement (i.e., session completion) impact results.

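### The four-asterisk note in 7.1 withdraws randomised intervention-arm non-starters from the study without saying they are still surveyed at 8 weeks, which works against the intent-to-treat inclusion in 11.2.3

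*Combined protocol and SAP*

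**What the plan says.** **7.1, four-asterisk note, first sentence:** "If participant does not start intervention within one month of baseline assessment, they will be withdrawn from the study by the study team". The withdrawal is from the study, not only from the intervention, and it is the team that acts.

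**Same note, next sentence:** "If a participant drops out of the intervention, they will be invited to complete the surveys if they want to (intent to treat". They may withdraw instead. Non-starters get no matching sentence.

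**7.2:** randomisation "occurs after a participant completes their baseline telephone survey". Section 5.4 gives the same order.

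**6.3:** controls complete the baseline and 8-week surveys and are offered STEP-UP only afterwards.

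**11.2.3:** "Following intent-to-treat principles, we will include all participants randomized to the intervention group".

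**11.2.2:** "The dependent variable in each model will be the value of the outcome at 8-week follow-up", with the baseline value as covariate. Section 11 describes no handling of missing outcomes.

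**6.10:** where participants withdraw or decline to finish, "every effort should be made to gather primary outcome data (pain interference". Contact stops for one group: "Participants who state that they wish to withdraw completely from the study will not be contacted further". People "randomized to the intervention but do not begin it will not be replaced" are mentioned only on the question of replacement.

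**6.8:** where the team ends participation because of acute illness or a change in disease severity, participants are contacted about outcome assessments. The section also allows the team to end participation for other reasons, including being too hard to reach. The sentence on outcome contact does not extend to those.

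**The concern.** The note sets up a loss of follow-up that can occur in only one arm and depends on behaviour after randomisation. If staff take withdrawal from the study to mean no further survey, intervention participants who never engaged disappear from the primary analysis. Their counterparts in the control arm, who would also not have started, remain. The two groups are then no longer the ones that randomisation produced.

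The analysis text cannot repair this. Section 11.2.3 says who should be analysed, but a person with no 8-week pain interference score contributes nothing to the model in 11.2.2. The conflict is operational: the schedule may prevent collection of data that the analysis plan assumes will be available.

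At stake is the preliminary effect estimate, which would describe those who started and not those who were offered the programme.

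**Working it through.** **Step 1: whom the rule can reach.** A month after baseline, everyone in the trial has been randomised (5.4, 7.2). The table in 7.1 marks randomisation in the column before week 0, which gives the same answer. Controls cannot start before their 8-week survey (6.3). The rule therefore acts only on the intervention arm.

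**Step 2: whether follow-up is still possible.** Taking a month as 30 days, the note acts at about day 30. The survey is due at day 56 and counts as non-missing for a further month, to about day 86. That leaves 56 − 30 = 26 days before the due date and 86 − 30 = 56 days before the window closes. The loss is avoidable.

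**Step 3: whether another section settles it.** Section 6.10 speaks of participants who withdraw or decline to finish, and does not say that withdrawal by the team is included for data collection. In 6.8 the outcome-contact sentence belongs to the illness cases. The note refers to neither section.

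**Step 4: size, for illustration.** The plan has no figure of its own to reproduce. From the documents: 40 participants at 1:1, so about 20 per arm; yardsticks of 2.5 points (section 2) and 3 points (11.2.2). Assumed:
- p, the share of the intervention arm that does not start: 2/20 or 4/20.
- D, the benefit in starters in T-score points: 2.5 or 3, borrowed from the yardsticks. Non-starters get no benefit.
- g, how much worse non-starters do at 8 weeks after baseline adjustment: 0 to 5.

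All randomised, complete follow-up: benefit = (1 − p) × D.

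Starters against all controls: benefit = D + p × g. Would-be non-starters remain among the controls and make that arm worse by p × g.

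Overstatement = D + p × g − (1 − p) × D = p × (D + g).

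| Non-starters | D = 2.5, g = 0 | D = 3, g = 5 |
|---|---|---|
| 2 of 20 | 0.10 × 2.5 = 0.25 | 0.10 × 8 = 0.80 |
| 4 of 20 | 0.20 × 2.5 = 0.50 | 0.20 × 8 = 1.60 |

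In the last cell, the all-randomised benefit is 0.80 × 3 = 2.40 and the starters-only figure is 3 + 0.20 × 5 = 4.00.

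**Direction.** If non-starters do better, g is negative. With D = 3 and g = −3 the error is zero. With D = 3 and g = −5 it is 0.10 × (−2) = −0.20 for 2 of 20, an understatement.

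**Partial response.** If r of k non-starters answer and resemble those who do not, the fix recovers r/(20 − k + r) × (D + g). With 1 of 2 answering, this is 1/19 × 2.5 = 0.13 to 1/19 × 8 = 0.42. With 2 of 4, it is 2/18 × 2.5 = 0.28 to 2/18 × 8 = 0.89.

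**How likely the rule is to act.** At assumed non-start rates of 5%, 10% and 20%, the chance of at least one non-starter among 20 is 1 − 0.95^20 = 64%, 1 − 0.90^20 = 88% and 1 − 0.80^20 = 99%.

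**The case against.** The strongest reply is that 6.10 already covers the case. Its heading is withdrawal from the study, its opening condition is general, it asks for every effort to obtain pain interference, and it bars contact only for people who themselves ask to leave completely. Section 6.8 shows the same intent where the team ends participation for illness. A non-starter who actively declines might also be counted as dropping out of the intervention and so be invited under the note's second sentence. All of this stands as evidence of intent. A reader might infer that 7.1 and 6.10 flatly contradict each other, and the documents do not support that. The general wording still does not reach the passive non-starter whom the team withdraws, and staff could follow either section.

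A second reply is that this is a pilot that 11.1 says is not powered for significance, and that the shift may be small beside sampling error. That is fair for many inputs. A reader might go further and infer a fixed ceiling in standard errors. None is available: the documents give no SD for this sample (10 is the T-score scaling) and the shift grows with the assumptions. With D = 3 and g = 8, 4 of 20 gives 0.20 × 11 = 2.2 points.

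A reader might also infer that the mean number of sessions will be overstated because non-starters are left out of it. No section says they are left out, so this is not an error in the plan.

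**Conclusion.** The concern holds as a gap between the schedule note and the analysis plan, and it should be fixed. Confidence is high on the text: the note withdraws randomised intervention-arm non-starters, does not say they are surveyed, and so works against 11.2.3, while 6.8 and 6.10 leave the matter unsettled. The effect estimate is harmed only if staff read the note as ending follow-up.

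Confidence in the size is low. The illustrated overstatements rest on an assumed non-start share, an effect borrowed from the yardsticks, no benefit in non-starters, and their doing no better than starters after adjustment. The documents support neither a known direction nor an upper bound. The case for acting is that an avoidable one-arm loss after randomisation can be removed cheaply.

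**What to change.** Reconcile the four-asterisk note, 6.8, 6.10 and 11.2.3 on one principle: ending participation in the intervention, whether the participant or the team decides it, does not by itself end outcome follow-up.

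- **7.1 note:** add that a randomised participant who has not started is still approached for the 8-week survey under the contact procedures in 5.6, unless they ask to withdraw completely.
- **6.8 and 6.10:** say that the effort to collect outcomes applies to every case in which the team ends participation, not only illness.
- **11.2.3:** say that all randomised participants with outcome data are analysed in the arm assigned.

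Whether a late start is allowed is for the sponsor to settle. Sessions should be recorded as actually completed, so that nobody who starts late is entered as having had none.

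**Cost.** About a sentence in each section. For each non-starter, 5.6 provides 5 contact attempts, a letter and 5 more attempts, with rescheduling until the one-month window closes and a separate sequence for disconnected numbers, so 10 calls is not a cap. Those who respond need an interview of about 45 minutes (5.4) and a $30 card. If 2 to 4 respond, that is 2 × 45 = 90 to 4 × 45 = 180 minutes and 2 × $30 = $60 to 4 × $30 = $120. The other downside is a possibly diluted effect estimate.
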